--	--

	
10. Time to a 2-point decrease in the WHO scale. Similar analyses as for time to death will be conducted.
 
11. Absolute values and absolute change in lymphocyte counts over time Summary statistics for both the absolute values and the absolute change from Baseline (day 1) will be tabulated.
 
12. Absolute values and absolute change in C-reactive protein levels over time Summary statistics for both the absolute values and the absolute change from Baseline (day 1) will be tabulated.
 
13. Absolute values and absolute change in D-dimer over time Summary statistics for both the absolute values and the absolute change from Baseline (day 1) will be tabulated (prognostic information: Zhou et al. Lancet 2020).
 
14. Absolute values and absolute change in log transformed levels of LDH over time Summary statistics for both the absolute values and the absolute change from Baseline (day 1) will be tabulated.
 
15. Time to hospital discharge Similar analyses as for time to death will be conducted.
 
16. Change in viral RNA over time Summary statistics for both the absolute values and the absolute change from Base-line (day 1) will be tabulated.
 
Other biomarker endpoints Other biomarker endpoints will be analyzed using descriptive statistics.

Sample size
	
186 patients (93 per group) will yield 80% power to detect a 20% absolute risk reduction in the primary composite endpoint, from 50% in the placebo group to 30% in the APN01 group at a two-sided alpha of 0.05. To consider patients who will be randomized but not treated a total of 200 patients (100 per group) will be enrolled.

Data Safety Monitoring Board (DSMB)
	
The study will be monitored by a DSMB.

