Similar analyzes as for 28-day mortality will be conducted. Patients without ≥ 2 improvement in WHO's 11-Point Score system will be censored on the last day of WHO scoring evaluation. For patients who died the observed time to a 2-point decrease until death will be considered; if a patient who died no 2-point decrease was observed, the patient will be censored on time of death.

11. Absolute values and absolute change in lymphocyte counts over time

Summary statistics for both the absolute values and the absolute change from Baseline (day 1) will be tabulated.

12. Absolute values and absolute change in C-reactive protein levels over time

Summary statistics for both the absolute values and the absolute change from Baseline (day 1) will be tabulated.

13. Absolute values and absolute change in D-dimer over time

Summary statistics for both the absolute values and the absolute change from Baseline (day 1) will be tabulated (prognostic information: Zhou et al. Lancet 2020).

14. Absolute values and absolute change in log transformed levels of LDH over time

Summary statistics for both the absolute values and the absolute change from Baseline (day 1) will be tabulated.

15. Time to hospital discharge

Similar analyses as for time to death will be conducted. Patients without hospital discharge will be censored on the last of hospital stay. Patients who died in the hospital will be censored on the day of death.

16. Change in viral RNA over time

Summary statistics for both the absolute values and the absolute change from Baseline (day 1) will be tabulated.

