Absolute values and absolute change in PaO2/FiO2 ratio over time

The PaO2/FiO2 ratio = PaO2 [mmHg] / FiO2

This will be evaluated on each visit for ventilated patients only. If entries are not changed compared to previous entries, no entry will be done within the eCRF.

If ventilation is ongoing and/or no stop date is available, the PaO2/FiO2 ratio will be considered until date of study completion/ discontinuation or date of death respectively.

Baseline is defined as first observation of PaO2/FiO2 ratio (individual start value). Basic statistics for the PaO2/FiO2 ratio for both the absolute values and the absolute change from baseline will be tabulated by day of ventilation. Daily means will be used when more than one assessment is available per day.

Absolute values and absolute change in notified sequential organ failure assessment score (mSOFA score) over time

The mSOFA score was introduced with protocol version 5.0 and is available for patients who are included with protocol version 5.0 and higher. For patients who are included with previous protocol versions (protocol version 4.0 and lower), mSOFA score is available from the time when protocol is in effect at the centers.

Basic statistics for the mSOFA score for both the absolute values and the absolute change from baseline will be tabulated by visit.

SOFA score (protocol version 4.0 and lower) will be listed only.

Time to a 2-point decrease in WHO's 11-Point Score system

Time to 2-point decrease [days] = Assessment date of first ≥ 2 improvement - Date of randomization.

Patients without documented 2-point decrease who completed the study or was early terminated or discharged from hospital before Day 28 will be censored at the date of last WHO assessment available.

Time to 2-point decrease will be analyzed using Kaplan-Meier estimates and plots, log-rank test, and Cox proportional hazards model (adjusted for center and age to derive hazard ratios and corresponding 95% confidence intervals).

Kaplan-Meier estimates and Log-rank test

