Kaplan-Meier table (product-limit "survival" estimates with 95%-CI, Standard error, Number of patient with event, Number of patient at risk) for Time to 2-point decrease [days], Kaplan-Meier Summaries of Event/Censoring (Number of patient with event, Number of patient censored, Total number of patients), Quartile Estimates (Median Time to Event, 1st Quartile, 3rd Quartile, 95%-CI) and Kaplan-Meier table ("survival" estimates with 95%-CI) for Timepoint (28 days). Time to 2-point decrease [days] will be displayed by a Kaplan-Meier-curve. Treatments groups will be compared with Log-rank test.

Cox proportional hazards model

The hazards ratio along with its associated 95% confidence intervals as well as parameter estimate and p-value (two-sided) will be reported.

Absolute values and absolute change in lymphocyte counts over time

Results of lymphocyte counts will be converted to standard unit before any calculation if needed. Conversion of all lab values will be described in a separate document.

Basic statistics for both the absolute values and the absolute change from baseline will be tabulated by visit.

Absolute values and absolute change in C-reactive protein levels over time

Results of C-reactive protein will be converted to standard unit before any calculation if needed. Conversion of all lab values will be described in a separate document.

Basic statistics for both the absolute values and the absolute change from baseline will be tabulated by visit.

Absolute values and absolute change in D-dimer over time

Results of CD-dimmer will be converted to standard unit before any calculation if needed. Conversion of all lab values will be described in a separate document.

Basic statistics for both the absolute values and the absolute change from baseline will be tabulated by visit.

Absolute values and absolute change in log transformed levels of LDH over time

Results of LDH will be converted to standard unit before any calculation if needed. Conversion of all lab values will be described in a separate document. Standardized results will be log transformed for this endpoint.

Basic statistics for both the absolute values and the absolute change from baseline will be tabulated by visit.

Time to hospital discharge

Time to hospital discharge [days] will be calculated as Date discharge from hospital - Date of randomization.

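### Time to a 2-point WHO improvement handles death as ordinary censoring, so its Kaplan-Meier quartiles and 28-day value do not describe the proportion of patients who improve

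*Protocol*

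**What the plan says.** Protocol section 8.7.1.2.5, endpoint 10, says that a patient without improvement "will be censored on the last day of WHO scoring evaluation". For deaths it adds: "if a patient who died no 2-point decrease was observed, the patient will be censored on time of death".

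SAP section 4.4.2 words the rule differently. It covers "Patients without documented 2-point decrease who completed the study or was early terminated or discharged from hospital before Day 28", and these patients "will be censored at the date of last WHO assessment available". Death is not named here, although the SAP does name it for time to hospital discharge.

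On method, the SAP says "Time to 2-point decrease will be analyzed using Kaplan-Meier estimates and plots, log-rank test, and Cox proportional hazards model". The output includes quartile estimates and a Kaplan-Meier table "for Timepoint (28 days). Time to 2-point decrease [days] will be displayed by a Kaplan-Meier-curve". No cumulative incidence or other competing-risk method is planned for this endpoint.

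The protocol's own cross-references differ. The body points to the methods for 28-day mortality, while the synopsis reads "10. Time to a 2-point decrease in the WHO scale. Similar analyses as for time to death will be conducted". The SAP follows the synopsis. SAP section 5 lists only a wording change for this endpoint, not the different censoring rule.

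**The concern.** Annex 1 of the protocol scores death as 10, the worst value. A patient who has died can no longer improve by two points. Kaplan-Meier censoring assumes that a censored patient would have gone on to improve at the same rate as those still followed. Applied to deaths, the curve describes a hypothetical population in which nobody dies, not the randomized patients.

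A reader of the 28-day value will take its complement as the chance of improving by Day 28, and the median as the time by which half have improved. Neither reading is right once some patients die unimproved. The comparison between arms also stops reflecting death: an arm that loses more patients before they can improve need not look any worse on this endpoint.

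**Working it through.** **Plan's own figures.** The documents give no improvement rate, mortality rate or power for this endpoint. The only power figure is for the primary composite (50% vs 30%, two-sided 0.05, 80%). The uncorrected chi-squared formula gives (1.960·√0.48 + 0.8416·√0.46)² / 0.20² = 93 per group, as stated. This does not bear on the present point. Since the composite includes death, those planning rates cap mortality but do not supply it, so a range is used.

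**Formula.** Let I be the true proportion improved by Day 28 and D the proportion who die unimproved, with constant cause-specific hazards. The cumulative improvement hazard over 28 days is

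H_I = −ln(1 − I − D) × I/(I + D).

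Kaplan-Meier with deaths censored then estimates 1 − exp(−H_I).

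**Results for an assumed I = 60%.**

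| D | H_I | 1 − KM | Excess (points) |
|---|---|---|---|
| 5% | 0.969 | 62.1% | 2.1 |
| 10% | 1.032 | 64.4% | 4.4 |
| 15% | 1.109 | 67.0% | 7.0 |
| 20% | 1.207 | 70.1% | 10.1 |
| 30% | 1.535 | 78.5% | 18.5 |

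For scale, the standard error of a 60% proportion in 100 patients is √(0.6 × 0.4/100) = 4.9 points. Lower improvement rates give smaller excesses: at I = 40% and D = 20% the excess is 5.7 points.

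**Illustration from the protocol.** Section 6.1 cites a UK inpatient cohort with 49% discharged alive and 33% dead at reporting. Using these as stand-ins for I and D gives H_I = 1.715 × 0.49/0.82 = 1.025 and 1 − KM = 64.1%, which is 15.1 points above 49%. Discharge is not the same as a 2-point decrease, and the cohort is not this population.

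**Median.** At I = 60%, D = 20%, the Kaplan-Meier median is ln 2 × 28/1.207 = 16.1 days. The true incidence is 0.75 × (1 − exp(−0.0575t)), where 0.0575 = 1.609/28. It reaches 50% at t = ln 3/0.0575 = 19.1 days.

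**What the comparison misses.** Give both arms the same improvement hazard, H_I = 1.032, with 10% mortality in one and 30% in the other.
- In both arms, 1 − KM = 64.4% and the cause-specific hazard ratio is 1.
- In the 10% arm, true improvement is 60.0%.
- In the 30% arm, the cumulative death hazard must be about 0.611. True improvement is then (1.032/1.643) × (1 − exp(−1.643)) = 50.7%.

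**Death date or last WHO visit.** Improvement can be recorded only on an assessment day. A patient who dies between two visits is in the risk set at the earlier visit and out of it at the later one under either rule, so the Kaplan-Meier values are the same. A simulation of 60,000 patients per rule on the visit schedule (I = 60%, D = 20%, separate random draws) gave 68.7% with censoring at death and 69.1% at the last visit, a gap due to the draws. About 56% had a recorded improvement. Holding deaths without the event to Day 28 gave 56.3%, equal to the recorded proportion.

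**Possible offset from discharge.** Suppose a fraction u of improvements goes unscored because the patient is discharged, and these patients are censored when they would have improved. Then 1 − KM = 1 − exp(−(1 − u)H_I). This equals 60% when u = 1 − 0.916/H_I, that is about 11%, 17% or 24% at mortality of 10%, 15% or 20%.

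**The case against.** The endpoint is one of 16 secondary endpoints that the protocol tests descriptively and in an exploratory way. Death is counted in the primary composite, in 28-day mortality and in time to death, and the WHO responder analysis at Days 7, 10, 14 and 28 treats death as non-response. Log-rank and Cox analyses with deaths censored are legitimate cause-specific comparisons. All of this stands and limits the weight of the point. It does not correct the tabulated probability or the quartiles. The responder analysis is not a full substitute either, because it also counts unassessed discharged patients as failures.

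The discharge rule is the strongest counter-argument. Censoring at the last WHO score can lose improvements that were never scored, and the offset above could cancel the excess from death. That stands as a limit on the net direction. It does not make the estimator right, because the two errors have different causes and need not balance.

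A reader might infer that the SAP's silence replaces the protocol rule and adds further bias. The SAP says it is based on protocol version 7.0 and declares no change here, so the protocol rule may still govern; in any case both censoring dates give the same values.

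A reader might also infer that the arm with more deaths gains on this endpoint. With equal true improvement of 60% and mortality of 20% vs 10%, Kaplan-Meier does show 70.1% vs 64.4%. That case requires an improvement hazard 1.207/1.032 = 1.17 times higher in the arm with more deaths. With equal improvement hazards, death is invisible rather than rewarded.

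**Conclusion.** The point holds for the Kaplan-Meier curve, quartiles and 28-day value: they do not estimate the proportion who improve or the time by which they do. Taking death alone, the proportion is overstated by 2.1 to 18.5 points for 5% to 30% mortality, and the median is too short. This assumes 60% true improvement and constant hazards; neither rate comes from the documents.

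The log-rank test and Cox model are sound if described as cause-specific, but they are blind to death. The documents do not support saying that the reported figure will be too high on balance, that the arm with more deaths benefits in general, or that deaths are hidden from the trial. Severity is minor to moderate.

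**What to change.** In SAP section 4.4.2, state that death without a prior 2-point decrease is a competing event. Replace the Kaplan-Meier curve, quartiles and 28-day value with the Aalen-Johansen cumulative incidence of improvement, accompanied by Gray's test or the subdistribution hazard ratio. If Day 28 is the only other reason for censoring, this is the same as holding patients who die unimproved in the risk set, without the event, to Day 28.

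Keep the log-rank test and the Cox hazard ratio with deaths censored at death, labelled cause-specific. The two sets of analyses need their own handling of deaths: a Cox model with deaths held to Day 28 is no longer cause-specific.

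List the change in SAP section 5 and align protocol section 8.7.1.2.5, including its cross-reference to 28-day mortality, which disagrees with the synopsis. Report how many patients in each arm are censored at discharge, because this change does not remove that source of error.

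The cost is SAP wording, alignment of the protocol text and a little extra analysis. Death dates are already used for time to death, so no new data are needed. The downside is a somewhat lower reported improvement rate.

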8.7.1.2.6 Biomarker Endpoints

Biomarker endpoints will be analyzed using summary statistics at each scheduled measuring time point for absolute values and for absolute change from baseline values. No statistical testing procedures will be applied to Biomarker analyses.

1. Angiotensin II (Ang II), Angiotensin 1-7 (Ang 1-7), Angiotensin 1-5 (Ang 1-5), renin and aldosterone, Angiotensin-converting enzyme (ACE), Angiotensin-converting enzyme 2 (ACE2), Angiotensin I (Ang I), Angiotensin 1-9 (Ang 1-9),
2. Cytokines: Interleukin 6 (IL-6), Interleukin 8 (IL-8), Soluble tumor necrosis factor receptor type II (sTNFrII), Plasminogen activator inhibitor type-1 (PAI-1), von Willebrand factor (vWF), Tumor necrosis factor- α (TNF- α)
3. Alveolar epithelial markers: Soluble receptor for advanced glycation end products (sRAGE), Surfactant protein-D (SP-D)
4. Endothelial markers: Angiopoietin-2
5. Change in clinical laboratory markers associated with poor outcome over time (e.g., lymphocyte counts, CRP, D-dimers, hsTnI (high sensitivity troponin))
6. NT-proBNP

8.7.1.2.7 Safety Endpoint

The safety evaluations will include analyses of AEs and SAEs, changes in vital signs, clinical laboratory assessments and in ECG parameters. The analysis of safety will be based on the SAF.

AEs

Pre-treatment AEs will be analyzed separately based on all patients included into the trial. AEs will be summarized by system organ class and preferred term according to Medical Dictionary for Regulatory Activities (MedDRA). The number of events, as well as the number and rate of affected subjects will be reported. AEs (system organ class and preferred term) will also be summarized by seriousness, by severity and by relationship to study medication. No statistical testing procedures will be applied to the analysis of AEs.

Individual patient data listings will be provided for all deaths, patients with other SAEs, unexpected adverse drug reactions (as confirmed by the sponsor's drug safety manager), discontinuation of IMP due to AEs, or premature trial termination due to AEs.

Vital signs

For vital signs, body temperature and body weight standard descriptive summary statistics will be calculated at each scheduled time point

Furthermore, standard descriptive summary statistics will be computed for the absolute change from baseline to each scheduled visit up to the last individual time point

Laboratory measurements

Laboratory data will be subjected to both a quantitative analysis (descriptive summary statistics) and qualitative analysis where frequencies of normal, above normal and below normal values will be computed.

The following analyses will be performed:

- Standard descriptive summary statistics will be calculated at each scheduled measuring time point
- Standard descriptive summary statistics will be calculated for the absolute change from baseline to each scheduled visit
- Frequencies of normal, above normal, and below normal values will be computed at each scheduled measuring time point
- Shift tables displaying changes with respect to the normal range between baseline and each scheduled visit will be provided
- A listing of all patients with abnormal (above normal or below normal) values at any time point will be given

Findings from ECG (12-lead)

Frequencies for the respective categories of (ab)normality will be tabulated.

A patient data listing of all clinically significant abnormal ECG values will be provided.

8.7.2 Determination of Sample Size

186 patients (93 per group) will yield 80% power to detect a 20% absolute risk reduction in the primary composite endpoint, from 50% in the placebo group to 30% in the APN01 group at a two-sided alpha of 0.05 when applying a two group Chi-Squares test. To consider patients who will be randomized but not treated a total of 200 patients (100 per group) will be enrolled.

9 CHANGES IN THE CONDUCT OF THE CLINICAL TRIAL OR PLANNED ANALYSIS

Modifications of the protocol are permitted only if they are authorized by the Sponsor and the PI in writing.

Deviations and changes to the study protocol will be classified by the Sponsor and the clinical trial center as:

Note-to-File: This refers to clarifications which are not considered changes of the protocol.

Study protocol amendment: This refers to changes of the protocol. If they fulfill the criteria as set out in the appropriate law, they need to be approved by the Ethics Committee(s) or the Competent Authority(ies) or both of them. Changes to the study protocol may also induce revision of the patient information sheet/informed consent form. Accordingly, patients undergoing trial assessment procedures at the time of implementation of the change have to be given the amended version and have to be asked for consent to continue in this amended trial.

9.1 Protocol Deviations

All protocol deviations will be tracked and actions will be defined, as feasible. All protocol deviations will be reviewed and classified in the DRM before data base lock and unblinding for the final analysis for assessment of their influence on the quality of the study analysis.

Protocol deviations (PD) are defined as follows:

Major PD:

- Informed consent procedure: ICF not signed and dated by patient/investigator
- Violation of an in- or exclusion criterion
- Randomization procedure
- Incorrect use of IMP (storage, preparation and administration)
- Use of forbidden concomitant medication
- Delayed reporting of serious adverse events

10 DSMB

A Data and Safety Monitoring Board (DSMB) will be established to protect the safety of study participants.

The DSMB will receive blinded CRF data in the form of tables and listings (prepared by an independent statistician), and adjudicate on patient status changes. Where appropriate, the DSMB may receive unblinded data (on a patient level) that should be reviewed in a closed session.

The data should include, but is not limited to, demographics, patient enrolment, baseline characteristics, AE data, SAE data (by severity and causality), laboratory data, protocol adherence, and patient withdrawals.

The DSMB will assess data quality and timeliness and patient's risk versus benefit. In addition, the DSMB will monitor external factors relevant to the trial, for example scientific and therapeutic developments that may affect participant safety or ethical status. Based on the observed benefits or adverse effects, the DSMB will make recommendations to the Sponsor concerning continuation, termination or modifications of the trial. Trial modifications may apply to an adjustment of dose and treatment duration, to the included trial population by adaptation of inclusion and/or exclusion criteria, to modifications on allowed or prohibited concomitant medications and medications to be considered for standard of care. The DSMB shall review overall diagnostic and therapeutic options available for COVID-19 patients and make recommendations whether the trial design needs to reflect these options through modifications in this trial.

The Sponsor will establish a DSMB charter document explaining the working procedures for the DSMB.

In addition, a DSMB meeting will be conducted whenever safety relevant data occur that might have an influence on the trial.

